1. INTRODUCTION

Obesity is a chronic disease characterized by an excessive body fat accumulation, which has a negative impact on health and affects the physical, social and emotional wellbeing. A double-blind study will be carried out using a weight loss program based on a low-fat, normoprotein, controlled ketogenic diet, followed by a metabolic adaptation process. During the weight loss process, psycho-emotional support and personalized physical activity supervision will be provided in order to modify lifestyle habits along with nutrition. In this study, supervision during 24 months of the weight lost is proposed to ensure the stability of the results obtained. In the initial phase where the diet process is fully controlled, the control group will receive the weight reduction program proposed by the WHO task force.

The weight loss program is developed according to the characteristics of each patient and includes medical control, dietary-nutritional supervision, introduction of a physical activity program and psycho-emotional support.

The primary objective of this study is to test the effectiveness, safety and security of this intervention method for weight loss and compare it with a conventional method for weight loss.

This document includes all the background information for the use of the so-called very low-calorie ketogenic diet, the hypotheses to be tested in this study, the methodology of how the objectives will be demonstrated and the statistical analyses used, the table of variables to be studied, the bibliography consulted and finally the materials used for data collection and management.

2. BACKGROUND.

Obesity is a chronic disease characterized by an excessive accumulation of body fat, which impacts health negatively and affects the physical, social and emotional wellbeing. It is a growing health problem with a high prevalence worldwide and a high impact in Mexico (1). According to a study conducted by the Food and Agriculture Organization of the United Nations (FAO), Mexico has become the country with the highest obesity rate, with 32.8% obese people, above the United States with 31.8% (2), such data definitely underestimates the problem in Mexico, since according to the National Health and Nutrition Survey (ENSANUT) 2018, 42.5% of men over 20 years old are overweight and 30.5%, are obese; while in women these figures correspond to 36.6 and 40.2%, respectively (3).

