So far, different variants of Blackburn's protein diet have been developed. Among them is the multidisciplinary Zélé program which, like the rest of the high-protein diets, is based on maintaining protein intake according to the calculated requirement, while reducing lipids and carbohydrate intake. However, this method does not only consist of weight loss by means of controlled ketosis, but also by patient re-education to promote changes in eating habits. . This program must be carried out under the supervision of a multidisciplinary group that includes a physician to control the possible side effects of ketosis, a nutritionist to supervise the nutritional habits and conditions, a

psychologist to strengthen and help maintain the patient's motivation for weight loss, and a physical trainer to adapt a personalized program for the preservation and strengthening of muscle mass.

The Zélé method consists of five stages: frank ketosis stage, mixed ketosis stage, transition stage, integral stage and maintenance. The ketogenic stage, in which a high-protein diet with high biological value (HBV) proteins is followed, supplemented with vitamins and minerals. In this stage, the expected weight is reduced by 70 to 80%, divided into frank ketosis and mixed ketosis, with a variable duration depending on the patient's initial weight and the kilograms to be lost, although for the purposes of the study a duration of between two and three months is proposed. In the transition stage, carbohydrates are incorporated with the purpose of leaving the metabolic state of ketosis. Later, in the integral stage, carbohydrates, natural proteins and fats are progressively incorporated, instilling in the patient the habits to achieve a balanced diet. In this stage, a loss of between 20% and 30% of the remaining excess weight is sought. Throughout the maintenance stage, with a supervised duration of two years, the patient is followed up and monitored to maintain the weight loss, with the advice of a team of dietitians and nutritionists.

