5. OBJECTIVES

5.1 *General Objective*

To evaluate differences in the response of weight, body composition and metabolic biochemical parameters among obese patients following a normoprotein low-fat controlled ketogenic diet compared to a balanced BIEM).

5.2 *Specific Objectives*

- Intra- and intergroup comparison of patient weight and BMI reduction between baseline and subsequent follow-up monitoring visits.
- To determine the percentage of patients with weight loss equal to or greater than 10% of initial weight and the time it took for patients to reach this figure.
- Evaluate the evolution of comorbidities associated with obesity (HT, hyperglycemia or diabetes, hypercholesterolemia, hypertriglyceridemia, apneas), control of clinical and analytical parameters and changes in medication during the weight loss process and during follow-up.
- To know the tolerability of the diet: Incidence of side effects during the development of the study,
- Safety of the intervention diet: appearance of analytical alterations, especially of the ionic profile, renal function and hepatic function, incidence of serious adverse events.
- Assess diet adherence and dropout rate and cause.
- To know patient satisfaction with the assigned nutritional program.

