
occurs first. And new biochemical evaluations when the decrease of Ketone Bodies below 0.4 mmol/l is detected or when patients have reached a loss of 60 to 70% of their overweight and one more when they reach their weight loss goal. Subsequently, only clinical and nutritional follow-up will be given along with psycho-emotional support and physical activity advice every 3 months up to 12 months and every 6 months up to 24 months.

7.2 Study design.

Longitudinal, Prospective, Controlled Randomized Clinical Trial.

7.3 Study population.

Patients of either sex, between 18 and 60 years of age, with a body mass index (BMI) between 30 and 35 kg/m².

7.4 Sample.

The sample will be obtained by open call through social media and all patients who come with their clinical analysis and meet the inclusion criteria will be evaluated until the sample number is reached. In order to obtain 95% power in this Controlled Clinical Trial and with a 95% CI, a 3:1 case-control ratio is established, considering a 35% attrition rate, 56 cases and 32 controls will be included and subsequently crossed to become cases. (Calculated with EPIinfo STATCALC for sample size)

Two blinded arms are proposed for the physician and the patient.

Obese patients assigned to the low-fat normoprotein controlled ketogenic diet group.

Obese patients assigned to a balanced hypocaloric diet. And who will subsequently be subjected to a controlled normoproteic low-fat ketogenic diet.

7.5 Inclusion, exclusion and elimination criteria.

7.5.1 Inclusion:

- Men and Women
- 18 to 60 years of age
- With BMI between 30 and 35 Kg/m²
- Who has not taken weight loss treatment in the last 6 months

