7.5.3 Elimination criteria

- Patients who drop out and decide to stop participating in the study.

(The patient has the right to withdraw from the study at any time, without the need to offer any explanation and without affecting the patient's future care or health care).

- The patient may also be withdrawn from the study at any time at the discretion of the investigator or the sponsor, for administrative or behavioral reasons or for missing two consecutive follow-up visits.
- Patients who during follow-up present any of the following criteria: Any serious adverse event
- Incoercible vomiting and nausea that do not allow following an oral diet.
- Worsening of diabetes control in patients with type II diabetes mellitus or insulin resistance
- Uncontrolled hypertension (SBP > 150 mmHg or SBP < 90 mmHg in successive repetitions).
- The reasons for abandonment of the study must be clearly documented in the registration notes. Any adverse reactions will be immediately reported to the Pharmaco-Surveillance system in charge of [name] [name] Principal Investigator.

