Arterial pH	Indicates the amount of hydrogen ions contained in the blood.	Determines the degree of acidity or alkalinity of the blood.	Quantitative, Ratio minimum 7.35 maximum 7.45	Registration form. Blood analysis
Lactic Acid	Substance produced by muscle tissue and blood cells. Lactic acid levels increase when oxygen levels decrease.	Acidic substance that accumulates in the blood and causes a decrease in pH, its ionized form is lactate.	Quantitative, Ratio 4.5 to 19 mg/l or 0.5 to 2.2 mmol/liter.	Registration form. Blood analysis
Anion Gap	Difference between anions and cations measured in the serum	Difference between anions and cations measured in serum	Quantitative, Ratio unit mEq/l minimum 8 max. 12	Registration form. Blood analysis
Excess Base	the amount of acid required to return the pH of an individual's blood to a normal value	the amount of acid required to return the pH of an individual's blood to a normal value	Quantitative, Ratio Minimum -2 maximum + 2	Registration form. Blood analysis

Satisfaction and Adherence				
Satisfaction Survey	Positive assessment of the different dimensions of the medical care received	Interrogation Very Satisfied to Very Dissatisfied	Categorical Nominal	Registration form.
Adherence to treatment	Taking medication according to the dosage of the prescribed schedule; and persistence, taking medication over time.	Interrogation Complied or did not comply with the program.	Categorical Nominal	Registration form. adherence to treatment

7.7 Data collection.

All data will be captured and recorded digitally in each of the queries through the Google Forms platform to consolidate the information in Google Sheets.

In the consultation, medical history data will be collected in the form of interrogation, weight will be determined through electronic scales, height through calibrated stadiometers, All measurements will be performed according to the WHO Physical Measurement Guide 2014 (www.who.int/surveillance/steps/Part3_Section4) Annex 1. In addition, a capillary determination of glucose and ketones will be performed at each clinical consultation. Once patients are drawn by lot they will be assigned to one of the control centers distributed in Mexico City, they will always have to go to the same control center (VIME). The consultation visits will be weekly for weight control and clinical check-up and every two weeks alternately for physical and psychological counseling.

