Blood samples will be collected in Specialized Clinical Laboratories according to NOM-253-SSA1-2012 and the laboratory sample collection manual in force in each laboratory. A venous sample will be taken to determine Complete Blood Biometry, Blood Chemistry of 27 elements, Basic thyroid profile, Glycosylated

7.8 Measuring instruments.

With all the data, a database will be built in Excel MS®. Patient satisfaction will be measured with the Likert Scale, which consists of 5 possible answers per item: very satisfied, satisfied, indifferent, dissatisfied and very dissatisfied. (attached)

7.9 Statistical analysis.

Descriptive statistical tests will be performed establishing general and group measures, determining variability measures such as standard deviation and Confidence Interval, comparative inferential tests will be performed within and between groups, for quantitative variables it is proposed as an initial T-test, which will be contrasted according to the conditions of normality and homoscedasticity of the sample. For qualitative variables, χ^2 is initially proposed, which will be contrasted according to the same conditions; one-way ANOVA and repeated measures ANOVA will also be used. Microsoft Excel 365 and SPSS V 21

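### Section 7.9 names no method that can handle patients with no observed time to 10% weight loss or with missing visits

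*Combined protocol and SAP*

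**What the plan says.** Section 5.2 sets as objectives the comparison of weight and BMI within and between groups over the follow-up visits, and the percentage of patients losing at least 10% of initial weight "and the time it took for patients to reach this figure". Section 7.7 schedules frequent weights: "The consultation visits will be weekly for weight control and clinical check-up".

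The plan expects incomplete data. Section 7.4 states: "considering a 35% attrition rate, 56 cases and 32 controls will be included and subsequently crossed to become cases". Section 7.5.3 places under its elimination criteria "Patients who drop out and decide to stop participating in the study", and also allows withdrawal after two consecutive missed visits. It does not say whether data collected before elimination are kept.

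For analysis, section 7.9 proposes descriptive statistics and then, "for quantitative variables it is proposed as an initial T-test", to be checked against normality and equal variance. Chi-squared is given for qualitative variables, and "one-way ANOVA and repeated measures ANOVA will also be used". Neither 7.9 nor any other section gives a survival method, a censoring rule, a missing-data rule or an analysis population.

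On the length of the controlled comparison, the Introduction says: "In the initial phase where the diet process is fully controlled, the control group will receive the weight reduction program". Section 2 says of the ketogenic stage, "although for the purposes of the study a duration of between two and three months is proposed". Section 7.10.1 fixes no time for frank ketosis, and no crossover date appears.

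**The concern.** A patient who has not reached 10%, has left, or has crossed over has no time to enter in a t-test. Unless a rule supplies a value, the test can use only those who reached 10%. That conditions on the outcome. In a limited window the reachers in either arm must all have been fast enough to reach 10% inside it, so their mean times are pushed together whatever the true difference in speed. This spoils the time even as a description.

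Repeated-measures ANOVA has a similar limit. In its standard form it uses only patients with every visit. If leaving depends on how much weight a patient is losing, the remaining patients no longer represent their arm, and the estimated weight difference can move in either direction. With the rule left open, it could also be chosen after the data are seen.

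**Working it through.** **Inputs from the documents.** 56 v 32 patients, 35% attrition (7.4), weekly visits (7.7), 10% threshold (5.2). Attrition alone leaves 0.65 x 56 = 36 and 0.65 x 32 = 21, about 57 of 88. Section 7.4 gives no effect size, standard deviation or event rate, so it has no figure that could be reproduced and used here.

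**Assumed inputs.** Each patient loses weight at a constant weekly rate, normal between patients with SD 0.25% per week. Dropout is exponential, 35% by the end of the window. The ketogenic mean of 0.90% per week is the low end of what the programme implies: 70% of excess weight over three months, counting excess above BMI 25 (assumed), for a patient at BMI 30 is 0.70 x 5/30 = 11.7% in 13 weeks, or 0.90% per week. Control means of 0.45 and 0.60 are assumed.

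**Who has an observed time at 12 weeks.** Reaching 10% needs at least 10/12 = 0.833% per week.
- Ketogenic, 0.90: P(Z > (0.833 - 0.90)/0.25) = 0.61, about 34 of 56 before dropout.
- Control, 0.45: P(Z > (0.833 - 0.45)/0.25) = 0.06, about 2 of 32 before dropout and 1.3 after it. Fewer than two controls have a time in about 62% of simulated trials.
- Mean times among reachers are about 10.1 v 11.1 weeks. The true medians are 10/0.90 = 11.1 and 10/0.45 = 22.2 weeks.

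**Power for the time (two-sided 5%, simulated).** The t-test uses reachers only; fewer than two in an arm counts as no rejection. Chi-squared counts dropouts as not reaching 10%.

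| Rates, % per week | Weeks | t-test | Chi-squared | Log-rank |
|---|---|---|---|---|
| 0.90 v 0.45 | 12 | 12-14% | 99-100% | 100% |
| | 26 | 98-99% | 92% | 100% |
| | 52 | 100% | 65% | 100% |
| 0.90 v 0.60 | 12 | 24-25% | 88-89% | 94-95% |
| | 26 | 93-94% | 45-49% | 99% |
| | 52 | 98% | 24% | 100% |

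**Sensitivity to these assumptions.**
- Over ketogenic rates of 0.90-1.6 and control rates of 0.30-0.60 at 12 weeks, the t-test ranges from 2 to 79% and log-rank from 95 to 100%.
- The recovery at 26 and 52 weeks needs loss to continue at the same rate; 0.90 x 52 = 47% of body weight is not realistic. If loss stops at week 13 in both arms, the t-test stays at about 28-40% at 26-52 weeks and chi-squared is 95-100%. If loss stops at week 18, they are 78-87% and 84-100%.
- If 80% v 30% or 70% v 40% would reach 10% by week 12 or by week 26, the t-test has 43-48% or 22-25%, chi-squared 93-97% or 51-61%, and log-rank 99-100% or 69-76%. Between 47 and 53 of the 88 have no observed time.
- With Weibull times instead (medians 10 v 20 weeks, shape 1.5), t-test and log-rank have 8% v 80% at 13 weeks, 33% v 97% at 26 and 90% v 99% at 52.
- With no true difference, the reachers-only t-test keeps about 5% false positives.

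**Weight at week 12.** Assumed: 12 weekly visits, residual SD 0.7, 35% dropout made more likely by smaller loss.
- True difference (0.90 - 0.45) x 12 = 5.4 points, same dropout rule in both arms: completers show 4.0-5.1 and a mixed model on all visits 5.4-5.5. Power is 98-100% either way.
- True difference (0.70 - 0.45) x 12 = 3.0, strong link: completers 2.3-2.6 with 81-84% power; mixed model about 3.1 with 97-98%.
- True difference 5.4, with poor responders leaving only the ketogenic arm: completers show 5.9-6.3.
- No true difference: no bias with equal rules. If dropout depends on loss in one arm only, the bias is -0.9 to +1.0 points with 9-22% false positives, against 5-7% for the mixed model.

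Scattered gaps matter too: if 5% of visits are missed at random, 0.95^12 = 54% of patients have all 12 weekly weights.

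**The case against.** The strongest reply is that the criticised analysis is not in the plan. Section 5.2 asks for the time to be determined, while its explicit between-group comparison is of weight and BMI. Section 7.9 begins with descriptive statistics and calls the t-test only initial. A reader might infer from the elimination criteria that the trial will compare reachers or completers only. The documents do not say so, and this stands. What remains is that no named method avoids the restriction, and that a mean time among reachers misdescribes speed even with no test attached.

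Second, the objective is partly served already. Chi-squared handles the percentage reaching 10%, provided all randomised patients form the denominator. A t-test with non-reachers set to the end of the window would do about as well as log-rank in the 80 v 30 and 70 v 40 settings, but has 76% against 100% at 52 weeks for 0.90 v 0.60. The plan states no such rule. Dropout rate and cause are to be assessed (5.2) and reasons documented (7.5.3), so the inputs for judging dropout will exist; their use in the analysis is not planned.

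Third, the 12-week window is assumed. Two to three months describes the ketogenic stage, not a stated control period. This also stands.

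**Conclusion.** The point holds as an omission with a better method available at almost no cost. Two stated objectives, the time to 10% loss and weight over visits, lack an analysis that can use all randomised patients, in a trial that itself expects 35% attrition and a crossover. Under the base assumptions at 12 weeks, a reachers-only comparison of times has about 12-25% power against 94-100% for log-rank. Log-rank was best or tied in every setting examined.

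Three stronger readings are not supported:
- A reader might take the table to mean that the t-test fails only in short windows and chi-squared only in long ones. That pattern depends on loss continuing unchanged, and it disappears when loss stops, as the staged programme in 7.10.1 suggests it may.
- The main weight hypothesis (H1) is not shown to be at risk. With a large effect the completers-only conclusion would not change.
- Inflated false positives for weight arose only where dropout depended on response in one arm. The documents neither support nor exclude that.

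Effect sizes, window and dropout mechanism are all assumptions. The plan should be amended, but this is not a fatal defect.

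**What to change.** In section 7.9:
- **Time to 10% loss.** Analyse from randomisation in all randomised patients by Kaplan-Meier with log-rank or Cox, censoring at dropout and at a stated crossover time. Add a sensitivity analysis counting dropouts as not reaching 10%.
- **Percentage reaching 10%.** Report at a fixed week before crossover, with all randomised patients as denominator.
- **Weight and body composition before crossover.** Instead of a t-test or repeated-measures ANOVA, use a likelihood-based mixed model on all available visits, including data collected before elimination. Include arm, categorical visit, arm-by-visit, baseline value and a parsimonious covariance; an unstructured matrix needs k(k+1)/2 parameters, 6 for 3 visits but 78 for 12. Add a sensitivity analysis for informative dropout.
- Do not extend the arm-by-visit model to laboratory values whose sampling is triggered by weight loss or ketone level (7.1).

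The cost is wording, a declared crossover time and some analyst time. The mixed model assumes that dropout depends only on observed data, and log-rank assumes uninformative censoring. The sensitivity analyses probe these assumptions but do not remove them, and they do not cover crossover that depends on response. Counting dropouts as not reaching also lowers log-rank power, for example to 54-65% from 69-76% at 70% v 40%.

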6. HYPOTHESIS

Assumption 1: **Weight Loss** .

H1: The use of the "Zélé method" (**Tx1**) allows a greater weight loss (*pp*) than a hypocaloric diet (**Tx2**) in the same time (*t*).

Assumption 2.

H2: Tx1 is safe and with low or no adverse effects.

Assumption 3. **Metabolic conditions**

H3: *pp* with Tx1 allows the regulation of metabolic syndrome and its components.

H4: The state of controlled ketosis that occurs with Tx1 does not change pH or raise blood lactate levels.

Assumption 4 . **Body Composition**.

H5. Tx1 will produce a selective loss of fat and preservation of muscle mass.

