Creatinine	Muscle protein degradation product	test that measures the level of creatinine in the blood	Quantitative, Ratio. mg/dl Quantity per cc Minimum 0.4 Maximum 1.3	Registration form. Blood tests
Urea	A substance formed by the body during the metabolism of proteins and nitrogenous compounds in the liver.	test measures the amount of urea in the blood	Quantitative, Ratio. mg/dl Quantity per cc Minimum 8 Maximum 54	Registration form. Blood tests
BUN	Amount of nitrogen from protein metabolism in the blood.	Test that measures the amount of urea nitrogen in the blood.	Quantitative, Ratio. mg/dl Quantity per cc Minimum 8	Registration form. Blood tests

			Maximum 54	
Uric Acid	Uric acid is an organic compound consisting of carbon, nitrogen, oxygen and hydrogen that is formed when purines are broken down by metabolism.	A test that measures the amount of uric acid in the blood.	Quantitative, Ratio. mg/dl Quantity per cc Minimum 2.4 Maximum 9.0	Registration form. Blood tests
Sodium	Electrolytes are minerals present in blood and other body fluids that carry an electrical charge. They affect the amount of water in the body, the acidity of the blood (pH), muscle activity and other important processes.	Determination of the amount of sodium in blood	Quantitative, Ratio. mEq/l Quantity per cc Minimum 135 Maximum 145	Registration form. Blood analysis
Chlorine	Electrolytes are minerals present in blood and other body fluids that carry an electrical charge. They affect the amount of water in the body, the acidity of the blood (pH), muscle activity and other important processes.	Determination of the amount of chlorine in blood	Quantitative, Ratio. mEq/l Quantity per cc Minimum 90 Maximum 110	Registration form. Blood análisis
Potassium		Determination of the amount of Potassium in blood	Quantitative, Ratio. mEq/l Quantity per cc Minimum 3.5 Maximum 5.5	Registration form. Blood análisis

Calcium		Determination of the amount of Calcium in the blood	Quantitative, Ratio. mg/dl Quantity per cc Minimum 8.5 Maximum 10.5	Registration form. Blood análisis
Phosphorus		Determination of the amount of phosphorus in blood	Quantitative, Ratio. mg/dl Quantity per cc Minimum 2.5 Maximum 4.5	Registration form. Blood análisis
Magnesium		Determination of the amount of magnesium in blood	Quantitative, Ratio. mg/dl. Quantity per cc Minimum 1.5 Maximum 2.5	Registration form. Blood análisis

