Albumin	Acute phase protein synthesized by the liver.	Amount of this protein in the clear liquid part of the blood.	Quantitative, Ratio. mg/dl. Quantity per cc Minimum 3.4 Maximum 5.4	Registration form. Blood analysis
Direct Bilirubin	A liquid of an oily nature, formed during the destruction of red blood cells, it is secreted by the liver whose function is to digest fatty foods.	Portion of bilirubin conjugated with glucuronic acid, moves freely in the bloodstream.	Quantitative, Ratio Normal value less than 0.3 mg/dl (0 less than 5.1 mcMol/l)	Registration form. Blood analysis

Indirect Bilirubin		Protein-bound portion that requires passage through the hepatocyte.	Quantitative, Ratio unit mg/dl Normal value Minimum 0.1 Maximum 0.5	Registration form. Blood analysis
Total Bilirubin		Sum of Direct B. and Indirect B. Indirect	Quantitative, Ratio unit mg/dl Normal value Minimum 0.1 Maximum 1.2	Registration form. Blood analysis
SGPT Transaminase	Aminotransferases, a group of enzymes that transfer amino groups from one metabolite to another, located mainly in the liver.	Alanine aminotransferase, predominantly hepatic, is released into the bloodstream when the liver is damaged.	Quantitative, Ratio unit IU/l Normal value Minimum 10 Maximum 41	Registration form. Blood analysis
SGOT Transaminase		Aspartate Amino Transferase, an enzyme found in the liver and muscle, is released into the bloodstream when the liver is damaged.	Quantitative, Ratio unit IU/l Normal value Minimum 5 Maximum 37	Registration form. Blood analysis
GGTP		Primarily hepatic enzyme released into the circulation when there is liver damage or biliary tract disease.	Quantitative, Ratio unit IU/l Normal value Minimum 11 Maximum 50	Registration form. Blood analysis

Serum Iron	Essential mineral for the production of hemoglobin, necessary for growth and development.	Test that measures the amount of iron in the blood.	Quantitative , Ratio minimum 60 mcg/dl Maximum 170 mcg/	Registration form. Blood analysis
Total Cholesterol	They are the most common type of fats in the body, coming mainly from saturated fats.	Test designed to measure the amount of free and protein-bound cholesterol in the blood.	Quantitative, Ratio minimum 100 mg/dl Maximum 200 mg/dl	Registration form. Blood analysis

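### Laboratory safety is framed as patients developing abnormal values, but the only method given for those variables compares means and does not answer that question

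*Combined protocol and SAP*

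**What the plan says.** Section 5.2 lists, as the safety of the intervention diet, "appearance of analytical alterations, especially of the ionic profile, renal function and hepatic function, incidence of serious adverse events". Section 6 adds "H2: Tx1 is safe and with low or no adverse effects", with no criterion, margin or tolerated rate.

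Section 7.6 defines the variables of those panels as quantitative: six electrolytes; creatinine, urea, BUN and uric acid; albumin, three bilirubins, SGPT, SGOT and GGTP. That makes 6 + 4 + 7 = 17. Potassium is entered as "Quantitative, Ratio. mEq/l Quantity per cc Minimum 3.5 Maximum 5.5" and SGPT as "Quantitative, Ratio unit IU/l Normal value Minimum 10 Maximum 41". No row records normal or altered.

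Section 7.9 is one general paragraph for all variables: descriptive measures with SD and confidence interval; "for quantitative variables it is proposed as an initial T-test", to be checked against normality and homoscedasticity; chi-square for qualitative variables; and one-way and repeated measures ANOVA. It does not tie any objective to a test. It does not say that the limits in 7.6 will classify patients, and it plans no shift table or out-of-range proportion.

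**The concern.** Whether alterations appear is a question about how many patients acquire an abnormal value. A t-test or ANOVA asks whether the arm means differ. The two can part company both ways. A mean can move while every patient stays normal. It can also stay put while some patients go low and others high.

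If the laboratory safety conclusion rests on the only method named for these variables, a flat mean may be reported as no alteration when patients have left the range, and a shift inside the range may be reported as an alteration. Neither result gives the reader the quantity that the objective names.

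**Working it through.** **The plan's own figure.** None is stated for laboratory safety. The sample size in 7.4 gives no endpoint, effect, SD or event rate, so it cannot be reproduced. This point does not depend on it.

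**Inputs.** From the documents: 56 and 32 patients and 35% attrition (7.4); potassium limits 3.5 to 5.5 mEq/l (7.6). With attrition, 56 × 0.65 = 36.4 and 32 × 0.65 = 20.8, so about 36 v 21. Assumed, because the documents give no values: potassium mean 4.4, SD 0.35, unaffected patients kept within 3.5 to 5.5, new abnormal values near 3.2 or 5.8. Two-sided 5% level; 10,000 simulated trials per setting unless stated. Fisher's exact test is applied to out-of-range counts.

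**1. Shift inside the range, nobody abnormal.** SE of the difference = 0.35 × √(1/56 + 1/32) = 0.35 × 0.2216 = 0.0776. A fall of 0.15 gives 0.15/0.0776 = 1.93 SE, and a fall of 0.25 gives 3.22 SE. Approximate power is Φ(1.93 − 1.96) = 49% and Φ(3.22 − 1.96) = 90%. Simulation, where the limits shorten the shift slightly, gives 46% and 86% (32% and 69% at 36 v 21).

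**2. Patients leaving in both directions: 10% low, 10% high.** Expected mean = 0.10 × 3.2 + 0.10 × 5.8 + 0.80 × 4.4 = 4.42, against 4.40. The difference is about 0.02 although a fifth of the arm is abnormal. The t-test rejects in about 2% of trials (2 to 3% at 36 v 21). It falls below 5% because the larger arm also has the larger variance. Fisher on incidence rejects in about 94% (60%).

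**3. Patients leaving in one direction: 20% low.** With no background abnormality: t-test 58%, Fisher 95% (39% and 59% at 36 v 21).

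**4. Sensitivity to background abnormality.** Steps 2 and 3 assume that controls are never abnormal, which favours the count. At 56 v 32:

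| Assumed background | One direction: Fisher v t-test | Both directions: Fisher v t-test |
|---|---|---|
| None | 95% v 58% | 94% v 2% |
| 5% in both arms | about 60% v 47% | about 60% v 3% |
| 5% in controls only (3,000 trials) | 44% v 54% | 43% v about 3% |

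The one-directional advantage shrinks and can reverse. The two-directional failure of the t-test remains.

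**5. Other assumed values.** With mean 4.5, SD 0.3 to 0.5 and a fall of 0.3, about 1 to 8% of patients are out of range and the t-test rejects in 99 to 79% of trials. With about 21% out of range, half each way, it rejects in 0.2%.

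**6. What a count would deliver.** 6/56 = 10.7% (exact 95% CI 4.0 to 21.9%), Fisher p = 0.08 against 0/32. 8/56 = 14.3% (6.4 to 26.2%), p = 0.047. 4/36 = 11.1% (3.1 to 26.1%), p = 0.29 against 0/21. Zero events in 56: upper limit 1 − 0.025^(1/56) = 6.4%.

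**7. Sampling.** Section 7.1 draws post-baseline biochemistry at milestones: 40% of overweight or 10 to 12 kg lost; ketones below 0.4 mmol/l or 60 to 70% of overweight lost; weight goal reached. An arm that loses more weight is therefore sampled more. At an assumed independent 5% abnormal rate per sample, three samples give 1 − 0.95³ = 14.3% with any abnormal value, against 5% for one sample, with no effect of diet.

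**The case against.** The strongest reply is that 7.9 never assigns laboratory safety to a t-test. It is a general and provisional paragraph. The table in 7.6 holds raw measurements, and other plainly proportional objectives, such as the share of patients losing at least 10% of weight, have no row there either. Chi-square is available if an alteration is treated as qualitative, limits are listed for these variables, and adverse effects are recorded at each visit. On this view the gap is one of specification.

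Much of that stands. A reader might infer that the sponsor has committed every laboratory safety variable to a t-test; the text does not go that far. What remains is that no alteration is defined, the listed limits are given no analytical role, and the only method named for the type these variables carry compares means. Replacing the t-test after assumption checks with Welch or a rank test would still compare location. Some limits in 7.6, such as triglycerides 100 to 500, look like data-entry ranges, so they cannot be taken as definitions of abnormality. Section 5.2 lists side effects and serious adverse events apart from analytical alterations and does not link them.

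Two technical objections also stand. In step 1 the t-test correctly detects a real mean difference; the fault lies in reading it as an alteration. And counting any abnormal value after baseline would bring in the sampling bias of step 7. Counting only new abnormality from a normal baseline would miss worsening in patients admitted with raised enzymes, since 7.5.2 excludes only those above 4 times the reference value.

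**Conclusion.** The concern holds as a mismatch between objective and analysis. It rests on the text of 5.2, 7.6 and 7.9 and not on the simulations, which show its size under assumed potassium values. A comparison of means can reject often (46 to 86% at 56 v 32) when nobody leaves the range. It has almost no power (about 2 to 3%) when patients leave in both directions, and this second failure persists with a 5% background abnormal rate.

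A reader might infer that a test on incidence is generally more powerful. That is not supported: for one-directional change the comparison runs from 95% v 58% to 44% v 54% depending on background, and the documents give no background rate. The case for counting is that it estimates what the objective names. At this sample size the useful output is the count with its interval, not another p-value. The plan should be changed before analysis.

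**What to change.** Add to 7.9, for each electrolyte, renal and hepatic variable:

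- State that an alteration is a value outside the reference range of the performing laboratory, with low and high counted separately.
- Report by randomised arm, before controls cross over, the number and percentage of patients out of range, with exact confidence intervals for each arm and for the difference.
- Give a shift table from baseline. For enzymes, grade it by multiples of the upper limit so that worsening from an already raised baseline is counted.
- Base the between-arm comparison on the same sampling occasion in both arms, the first post-baseline profile. Report by arm the number of patients sampled, samples per patient and time to sampling. Give counts over all post-baseline samples descriptively only.
- Keep mean comparisons as supportive.

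The cost is a few lines in 7.9 and a derived classification per laboratory test, with no new samples. Two limits remain. Intervals will be wide: up to 6.4% for zero events in 56, and 1 − 0.025^(1/36) = 9.7% for zero in 36. Patients who never reach a milestone have no post-baseline value, and the first profile may fall at different times in the two arms, so the sampling figures must be read beside the counts.
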